In order for the modified gait pattern to be adopted during activities of daily life, it may be necessary for it to become autonomous, such that it is adopted without (excessive) cognitive demand. Achieving such a stage of learning may require a change in the type and frequency of the feedback given to the patients between the first (initial) training session and last training session. In addition, regular home-based training using the modified gait pattern may help to internalise the new gait pattern and reduce the tendency to revert back to the original pattern. In this way the benefits of the training program may have increased applicability and may lead to a longer term reduction in medial knee pain. To examine the effects of training or skill acquisition on motor learning, dual tasking scenarios can be used. This allows an estimation of the cognitive demand of the primary task to be estimated by measuring the effect on the task of adding in an additional task [60]. The secondary task may be a cognitive task, such as a memory test, or an additional motor task. Previous research in this area has tended to focus on neurological pathologies, in particular CVA, Parkinson's and Alzheimer's. However, in the orthopaedic population, Hiyama et al. [61] showed that a four week walking program improved patient's dual tasking performance compared to a control group. This suggests that the cognitive demand for performing the motor task (walking) was reduced, allowing improved performance in the secondary task. This may have important consequences in activities of daily living (ADL).

Studies investigating the effects of gait modifications on KAM (including the proposed study) are usually conducted under idealised conditions, for example within a laboratory setting with an even, level flooring or on a treadmill at fixed pace with the belts level or at a fixed gradient. To increase the similarity to the real world environments, and hence improve applicability in the real-world environment, the addition of obstacles or such like to the laboratory environment may be necessary. Obstacle avoidance has been shown to be reduced in patients with knee osteoarthritis, therefore increasing the likelihood of trips [62].

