2. OBJECTIVES

The primary objective of study A is:

• To evaluate the use of real-time visual and audio feedback on the knee adduction moment during gait in patients with knee osteoarthritis to decrease the biomechanical load on the knee via implicit learning and explicit instructions.

The secondary objective of study A is:

- To evaluate changes in the kinematic patterns and electromyographic patterns between baseline (without feedback) and modified (with feedback) gait patterns.
- To identify factors based on the demographic, radiographic and baseline kinematics which increase the likelihood in reducing the KAM using the biofeedback training method.

The primary objectives of study B are:

- To provide proof-of-concept for the use of real-time feedback as a clinical intervention on gait retraining to decrease the biomechanical load on the knee in patients with knee osteoarthritis during a 6 weeks training and 3 and 6 months follow-up.
- To assess changes in pain and function as a result of the biofeedback gait training programme; this will be measured using the WOMAC questionnaire and NRS pain scale. Pain and function are important outcome measures for the patient and are therefore included as additional primary outcome measures.

The secondary objective of study B is:

i) To estimate the reduction in cognitive demand (and hence the extent of motor learning) of the gait modifications over the six week retraining period.

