5.1.3 Other study parameters (if applicable)

Other study parameters are muscle strength, activity limitations, self-reported knee joint stability, performance-based activity limitations (GUG, 10-m walk test), co-morbidity, duration of (gait) complaints and radiographic Kellgren/Lawrence score.

A series of demographic variables will be obtained including age, gender, height, weight.

Other study parameters specific to study B are satisfaction and adherence of the gait modification. The change in cognitive demand of the gait modifications between the initial and final training weeks will also be considered in study B.

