In step 4, explicit verbal instructions will be given on the gait pattern in addition to the realtime visual KAM feedback to further develop a pattern that can be sustained in daily life (e.g. toe-in/out <15deg). Hunt and Takacs (2014) mentioned that a toe-out position of \pm >15 (difference from baseline) is difficult to obtain [3]. Reference values of step width and medial thrust/ frontal plane position of the knee, will be obtained from the baseline trial and the initial trials with feedback on the KAM. This will enable threshold limits to be set such that the step width (for example) is not increased to an excessive degree. The values of all of the kinematic and kinetics will be available for the researcher in real time. In this way, the instructions to the patient can be adapted to suit the individual patient, based on objective information. In step 6, the optimal gait pattern will maintained by the subject without any feedback.

| Condition | Description | Time | Purpose | Recording |
|-----------|--|---|--|-----------|
| | | | | time |
| | | | | (seconds) |
| 0 | Acclimatization to treadmill | Up to 4 minutes | To determine the average (mean) speed of walking for use in training period | 0 |
| 1 | Baseline condition- own shoes | 60 seconds minutes | 15 seconds familiarization plus45 seconds recording time | 45 |
| 2 | Training phase | Up to 21 minutes depending on the week | This will be based on the results of study A. Explicit guidance will be given as required. Frequency of the feedback will be adjusted if necessary to avoid dependence on it and encourage motor learning. | 0 |
| 3 | Measurement without feedback while new pattern is applied | 60 seconds | 15 seconds familiarization plus 45 seconds recording time | 45 |
| 4i* | Measurement without feedback, -with dual tasking (Stroop test/ memory test) | 75 seconds | 30 seconds familiarization plus 45 seconds recording | 45 |
| | • | | | |

The following protocol will be used in Study B for each of the two sub-groups.:

| 5 | Advice for home | ~8 minutes | Clinician/ physio to offer advice | 0 |
|---|-----------------|------------|-----------------------------------|---|
| | training | | for home training | |

Steps 0,1,2,3 and 5 repeated at weekly intervals.

* Steps 4i, 4ii and 5 will only be applied during week 4 to 6, thus the time taken for training sessions 1 to 3 will be shorter.

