| | | | the knee | appropriate for this patient | bend your knee and move your knee towards the centre of your body. | your knee and move the marker on your knee towards the centre of your body | with target region – knowledge of performance 2) Target value for medial knee thrust based on MTK _{implicit} shown, with reward when target is reached- knowledge of results |
| Trunk lean/ sway | TS _{implicit} ≫ TS _{baseline} | | | Trunk sway being used excessively to control KAM | Reduce trunk sway | | No feedback given |

| | | Study | Study B | | | | |
|-----------------------|---|-------|---------|----|----|--------------|--|
| | A | | | 1 | | 1 | |
| | | M1 | M1 | M2 | М3 | M4 | |
| | Consent | ✓ | | | | | |
| | Basic demographics | ✓ | | | | | |
| | WOMAC | ✓ | ✓ | ✓ | ✓ | ✓ | |
| | NRS pain over last week | ✓ | ✓ | ✓ | ✓ | ✓ | |
| | Knee instability | ✓ | | | ✓ | ✓ | |
| | Knee confidence | ✓ | | | ✓ | ✓ | |
| | | | | | | | |
| Questionnaires | NRS pain during walking on treadmill | ✓ | 1 | ✓ | ✓ | ✓ | |
| | Feedback on feedback | ✓ | | | | | |
| | Satisfaction with the program | | | | | | |
| | Compliance with the modified | | | ✓ | ✓ | ✓ | |
| | gait pattern | | | | | | |
| | Timed GUG | ✓ | ✓ | | ✓ | \checkmark | |
| | 10m walk test (fast) | ✓ | ✓ | | ✓ | ✓ | |
| Activity/ performance | 10m walk test (comfortable) | ✓ | ✓ | | ✓ | ✓ | |
| lesis | Muscle strength | ✓ | ✓ | | ✓ | ✓ | |
| | | | | | | | |
| | Baseline own shoes | ✓ | ✓ | ✓ | ✓ | ✓ | |
| | | | | | | | |
| | Implicit learning | ✓ | | | | | |
| | Explicit learning 1 | ✓ | | | | | |
| | Explicit learning 2 | ✓ | | | | | |
| Gait and balance | Explicit learning 3 | ✓ | | | | | |
| | Training | | ✓ | ✓ | | | |
| | Retention | ✓ | ✓ | ✓ | | | |
| | Dual tasking- cognitive | | ✓ | ✓ | ✓ | \checkmark | |
| | Dual tasking- physical | | ✓ | ✓ | ✓ | \checkmark | |
| | | | | | | | |

14. APPENDIX A2: Patient measurements at each stage of the patient journey

| Study B | | | | | | | | |
|---------|-----------|----|----|------------|-----|--|--|--|
| T1/ | T2 | Т3 | Τ4 | T 5 | T6/ | | | |

| | M1 | | | | | M2 |
|--|----|---|---|---|---|----|
| NRS pain during last week | ✓ | ✓ | ✓ | ✓ | ✓ | ✓ |
| NRS pain during walking on treadmill | ✓ | ✓ | ✓ | ✓ | ✓ | ✓ |
| Activity levels over last week- step counter | ✓ | ✓ | ✓ | ✓ | ✓ | ✓ |
| | | | | | | |
| Difficulty and "normalness" of learned walking | ✓ | ✓ | ✓ | ✓ | ✓ | ✓ |
| pattern | | | | | | |

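### Section 5.2 confines the dual-task trials to weeks 4 to 6, Appendix A2 schedules them from week 1, and the choice decides whether Study B's secondary objective can be estimated

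*Protocol*

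**What the plan says.** Section 2 lists one secondary objective for Study B: "To estimate the reduction in cognitive demand (and hence the extent of motor learning) of the gait modifications over the six week retraining period". Section 5.1.3 names the contrast, a change "between the initial and final training weeks". Section 1 identifies the instrument: "To examine the effects of training or skill acquisition on motor learning, dual tasking scenarios can be used". Section 7.3 plans a linear mixed model for changes in gait during dual tasking.

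Two places set the schedule for those trials:

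- **Section 5.2, Study B table.** Step 4i is the cognitive dual-task trial (Stroop or memory test, no feedback). The footnote states "Steps 4i, 4ii and 5 will only be applied during week 4 to 6" and infers that training sessions 1 to 3 take less time. The line just above it reads "Steps 0,1,2,3 and 5 repeated at weekly intervals", which leaves step 4 out of the weekly steps.
- **Appendix A2, first table.** The row "Dual tasking- cognitive" and the physical dual-task row below it are blank for Study A and ticked for Study B at M1, M2, M3 and M4.

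Section 3 places M1 in week 1 and M2 in week 6, with M3 and M4 at the 3- and 6-month follow-ups.

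**The concern.** A change from the first to the last training week needs a measurement in the first training week. Section 5.2 rules that measurement out for the dual task; Appendix A2 asks for it. The protocol does not say which of the two takes precedence.

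The loss would be permanent. The week 1 value describes a patient who has only begun to learn the modified gait. By week 4 the patient has completed three training sessions and practised at home, and the early state can no longer be observed. The contradiction therefore has to be resolved before the first Study B visit; it cannot be repaired at analysis.

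**Working it through.** The plan states no figure on this point, so there is nothing to reproduce. The check sets the schedules side by side for the cognitive dual task.

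| Time point | Section 5.2 | Appendix A2 |
|---|---|---|
| Study A | none in the condition table | blank |
| Week 1 (T1/M1) | no | yes |
| Weeks 2 and 3 | no | not scheduled |
| Weeks 4 and 5 | yes | not scheduled |
| Week 6 (T6/M2) | yes | yes |
| 3 and 6 months | yes | yes |

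1. **Where they agree.** The two schedules coincide only at week 6 and the two follow-ups.
2. **Estimability.** The target is the mean week 6 value minus the mean week 1 value. Under Appendix A2 both terms are observed. Under section 5.2 the week 1 term is missing for every patient by design.
3. **Can Study A stand in?** No. Its condition table in section 5.2 has no dual-task condition, and its Appendix A2 cell is blank.
4. **Can the mixed model in section 7.3 stand in?** No. It can handle a value missing for some patients, but a time point observed in nobody contributes no data. Running weeks 4, 5 and 6 back to week 1 would rest wholly on an assumed learning curve.
5. **Can step 3 stand in?** No. It is the single-task trial of the new pattern and is recorded weekly, but it does not load attention and so does not measure cognitive demand by the method section 1 describes.
6. **Could the footnote cover training sessions and Appendix A2 measurement sessions?** No. T1 and M1 are one visit: section 3 puts both in week 1, and the second table of Appendix A2 heads them as one column. The footnote also says *only* and shortens session 1 as a result.

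Cost at week 1 for step 4i: 30 seconds of familiarisation + 45 seconds of recording = 75 seconds.

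The same footnote conflicts with the protocol a second time. It limits step 5 (home-training advice) to weeks 4 to 6, while the line above repeats step 5 weekly.

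**The case against.** The strongest reply is that the plan already contains a workable schedule. Section 3 and the opening of section 5.2 both send the reader to Appendix A2 for what is measured when, and Appendix A2 fits the objective. On that view this is a drafting slip. Part of this stands: it would be wrong to say outright that Study B has no starting value, or that all 30 patients lose theirs. That follows only if the section 5.2 footnote governs. But section 5.2 offers Appendix A2 only as an overview, and the footnote is the more operational instruction, with a stated consequence for session length.

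It can also be said that sections 2 and 5.1.3 speak of cognitive demand, not dual tasking. That is correct. The link comes from section 1, which says dual tasking can be used. It is a fair inference, since no other measure is tied to this objective. Appendix A2 has a weekly rating of how difficult the learned pattern feels, but nothing presents it as a measure of cognitive demand.

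Three stronger readings might be inferred, and the documents do not support them:

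- **A share of the learning that goes unobserved.** The protocol gives no learning curve. If the change were linear, weeks 4 to 6 would cover 2 of the 5 weekly intervals from week 1 to week 6, or 40%; other assumed curves give other values. No percentage is claimed here.
- **Selectively missing week 1 data.** Experiments and training take place in one laboratory, and nothing suggests that staff would follow different sections or that missingness would depend on the patient.
- **Loss of all of sessions 1 to 3.** The named contrast needs only the first and last weeks, and Appendix A2 does not schedule dual tasking in weeks 2 and 3 either. Week 1 is the loss that matters.

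**Conclusion.** The contradiction is real and decides whether a stated objective can be met. If section 5.2 is followed, the week 1 to week 6 change in cognitive demand cannot be estimated for any Study B patient; if Appendix A2 is followed, it can.

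This rests on two readings: that dual tasking is the intended measure of cognitive demand, and that M1 and T1 are the same visit. The documents support both.

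The reach is limited. Cognitive demand is a secondary objective in section 2 and appears among the other parameters in section 5.1.3. The sample size is based on KAM, and neither the KAM endpoint nor the primary pain and function outcomes are touched. The step 5 conflict is a separate wording matter and has no bearing on the dual-task conclusion.

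**What to change.** Amend the section 5.2 footnote so that the dual-task measurements (cognitive step 4i, and the physical task as ticked in Appendix A2) are recorded at week 1 (M1) and week 6 (M2). Remove the inference that session 1 is shorter because it has no dual task. Check the design scheme in section 3, whose text is damaged in the copy reviewed, and amend it too if it repeats the restriction. The week 1 versus week 6 change can then be estimated in the linear mixed model already planned in section 7.3; no new method is needed.

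The cost is 75 seconds of walking for step 4i, plus the physical dual-task trial (duration not legible in the copy reviewed), at a visit already planned.

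Separately, reconcile the footnote's limit on step 5 with the line above it. Which frequency of home-training advice is intended is for the investigators to state.

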5. METHODS

5.1 Study parameters/endpoints

5.1.1 Main study parameter/endpoint

The main study parameter will be the **external knee adduction moment (KAM).** The KAM is determined by the ground reaction force (GRF) and its lever arm in the frontal plane and considered a surrogate for medial compartment loading.

The two KAM peaks (in early and late stance) have been linked to the presence, severity, and progression of knee OA [10;15]. Gait modification (e.g. toe-out/in, trunk sway, step width, medial thrust, hip rotation etc.) have been shown to influence the KAM (peaks in early and late stance, KAM during mid-stance and KAM impulse (area under curve) [12;13;43].

For study B, the change in KAM over the 6 weeks training period and at 3 and 6 month follow-ups will be evaluated.

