5.2 Study procedures

The below text describes the individual measurements that will be undertaken during Study A and Study B. For an overview of what will be measured in Study A and at each interval of Study B, see APPENDIX A2.

Gait Real-time Analysis Interactive Lab (GRAIL)

Experiments and training will be conducted on the GRAIL, Gait Real-time Analysis Interactive Lab (MOTEKForceLink), situated in the VR-laboratory of the VU medical centre, rehabilitation department. This high-tech gait lab consists of a virtual reality system for gait biofeedback.

The GRAIL uses a dual-belt instrumented treadmill, an immersive virtual reality environment, an optoelectronic movement recording system with wireless, light-reflecting markers for accurate (<0.5 mm) and easily analysable 3D motion capture (Vicon), electromyography (EMG, ZeroWire), software for system integration and control (D-Flow [83]), and software for real-time musculoskeletal modelling (Human Body Model HBM [43;84]).

The instrumented treadmill has two full 6D force plates underneath each belt. This configuration enables measurement of ground reactions forces under each foot separately

during walking. This is needed as an input to calculate real-time joint kinetics (net joint moments and joint load), kinematics and muscle forces.

The length of the treadmill is 2.20m to accommodate almost unrestricted walking, and to allow for some positional changes of the subject during walking at self-paced walking speed (i.e. the speed of the belt is automatically adjusted to the subject's comfortable walking speed [85]). The GRAIL offers the possibility to obtain many consecutive strides, which can each be measured accurately. Subjects will wear a safety harness during the trials, to protect them in the event of a fall.

Figure 1. Gait Real-time Analysis Interactive Lab, VUmc

Marker placement

Prior to measurement, 42 markers for the reconstruction of the position and orientation the lower limb bones in space (kinematics) will be placed on the subjects. During the measurements, the Human Body Model [84] will be used to calculate real-time kinematics and kinetics that can be used for the real-time feedback.

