Note, the patient can take a break at any time during the training/ assessment The total walking time will depend on the week number; see also Figure 2, which presents the faded feedback approach that will be used. The total duration of the training sessions will be increased during the course of the intervention, with a decrease in the feedback time. This approach (termed faded feedback) has been shown to improve motor learning {Winstein, 1990 265 /id} and has been implemented successfully in several studies related to biofeedback for gait retraining including Barrios et al. (2010), Hunt and Takacs (2014) and Shull et al. (2013).

Figure 2: Progression of training and feedback time during the study

In step five, the researcher will provide the patient with home training advice based on the gait retraining methods used in the preceding stages. This may include advice on how to stand up from a chair or how to ascend/ descend stairs. It is important the home training advice complements the advice provided during the gait re-training session.

In addition to the weekly sessions described above, further measurements will be obtained 3 and 6 months after the last training session. This final measurement will consist of both a baseline measurement and replication of the learned pattern, with and without the cognitive dual tasking.

Real-time visual feedback will be provided on the semi-cylindrical screen of the GRAIL. Various types of feedback are available: e.g. bar plot, polar plot, colour change, graph [43] or a number of the actual peak value. Figure 3 shows some examples of feedback that have been used previously in gait modification protocols on the GRAIL. However, other types of visual feedback, such as footsteps indicating desired foot progression angle and/ or step width have been proposed for this study, and have been given a favourable opinion by clinicians. Audio feedback will also be evaluated in Study A.

Figure 3: Examples of different types of real-time visual feedback that can be used on the GRAIL [43].

Knee pain

Knee pain (study A and B) over the past week will be assessed by an 11 point numeric rating scale (NRS; 0 -10), with higher scores representing more pain. Patients will be asked: "What was your pain rating on average over the past week?"

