Muscle strength will be assessed in study A and at the beginning and end of the training period and at 3 and 6 months follow up in study B, specifically for the knee flexors and extensors using an isokinetic dynamometer (Humac Norm, CSMi, Boston, USA). Quadriceps and hamstrings strength are measured isokinetically at 60⁰/second. All patients will be assessed according to a previously described device and protocol [88]. The mean in Nm per kg body weight (Nm/kg) for quadriceps and hamstrings strength of the right and left maximum voluntary contraction obtained from three measurements will be used for analysis.

Self-reported stability

Knee instability will be measured in study A by questioning the perception of knee stability [89] and by questioning the perception of knee confidence during walking [90]. Self-reported knee instability has been defined as the sensation of an episode of buckling, shifting or giving way of the knee in the previous three months [89]. Persons reporting knee instability will be additionally asked for the number of episodes of instability, whether these episodes concerned the left, right or both knees, if any episodes had resulted in a fall, and the

particular activity that induced an episode of instability [26]. Also the amount of falls related to the perception of knee instability will be assessed.

Activity limitations

A self-report questionnaire will be used to assess limitations in daily activities (study A and at the beginning and end of the training phase in study B and at the 3 and 6 months follow us): the Western Ontario and MacMasters Universities Osteoarthritis Index (WOMAC) [91;92]. The Dutch version of the WOMAC will be used [93]. The WOMAC is a disease specific measure of pain, stiffness, and physical function for individuals with OA of the knee. The WOMAC, with a possible range of 0-96, includes 5 items related to pain, 2 items related to stiffness, and 17 items related to physical function (PF). Each item is scored on a 5-point Likert scale. Reliability and validity of the WOMAC have been established [93]. Higher scores on the WOMAC represent greater reduction in functional ability. The ICC for Dutch WOMAC physical-functioning is 0.92 [93].

Performance-based activity limitations

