7. STATISTICAL ANALYSIS

7.1 Primary study parameter(s)

To assess the effect of feedback on external knee adduction moment (KAM) a linear mixed model and repeated measure analysis of variance will be used. Four outcomes parameters will be extracted from the gait cycle, i.e. the KAM peaks at early and late stance with the corresponding KFM values, the KAM during mid-stance, and the impulse (area under curve in %BW*H*sec) [13;43]. In Study A comparison will be made between baseline and gait modification conditions; in Study B the change over time will be calculated for both baseline and replication of learned pattern. The associations between the changes in KAM, KFM, kinematic pattern and pain will be determined.

To identify the factors which predict whether an individual is likely to achieve a good result using the bio-feedback training method, a linear mixed model will again be used.

Statistical significance will be accepted at p-values of less than 0.05. All analyses will be performed using SPSS software, version 21.0 (SPSS, Chicago, IL).

Changes in pain and function over time in study B, as reported using the WOMAC questionnaire and NRS pain scale will also be assessed using a linear mixed model. Patient reported pain and function will be compared during a no-treatment period (immediately following assessment for Study A) and also over time during the intervention period.

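### Appendix A2 schedules no single-task walk with the learned pattern at 3 and 6 months, although section 5.2 requires it and the section 7.1 primary analysis uses it

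*Protocol*

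**What the plan says.** Section 5.1.1 defines the Study B main parameter over both training and follow-up: "the change in KAM over the 6 weeks training period and at 3 and 6 month follow-ups will be evaluated". Section 7.1 then splits the analysis by walking condition: "in Study B the change over time will be calculated for both baseline and replication of learned pattern".

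Section 5.2 describes how the data arise. In the weekly Study B sessions, step 3 is "Measurement without feedback while new pattern is applied", with 15 seconds of familiarisation and 45 seconds of recording. After training, "further measurements will be obtained 3 and 6 months after the last training session", and the content of those visits is given as "This final measurement will consist of both a baseline measurement and replication of the learned pattern, with and without the cognitive dual tasking".

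For the visit-by-visit schedule, section 5.2 refers the reader elsewhere: "For an overview of what will be measured in Study A and at each interval of Study B, see APPENDIX A2". Section 3 points to the same appendix twice. In the A2 table the gait rows ticked at M3 and M4 are own-shoes baseline, cognitive dual tasking and physical dual tasking. The 'Retention' row is ticked for Study A, M1 and M2 and is empty for M3 and M4.

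**The concern.** The text and the schedule disagree on whether patients walk with the learned pattern, undisturbed by a second task, once training has stopped. Whether the trained gait persists is part of the Study B primary objective, and the single-task walk measures it most directly. It is also the only follow-up walk recorded under the same condition as step 3 of the training sessions.

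A visit run from A2 would produce a learned-pattern KAM only under dual tasking. Set against single-task values from weeks 1 to 6, any difference would mix the passage of time with the effect of the second task. The protocol's own introduction treats dual tasking as a means of detecting cognitive load on gait, so it cannot be assumed to leave KAM unchanged. A walk that was not recorded cannot be recovered afterwards.

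**Working it through.** No figure in the protocol is disputed here. The check sets the schedule beside the text, column by column.

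**Column order in A2.** The columns are Study A, M1, M2, M3, M4. Two rows confirm the alignment: own-shoes baseline is ticked in all five, and compliance with the modified pattern is empty for Study A and M1 and ticked for M2 to M4, as one would expect of a question about a pattern already in use.

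**Gait rows in A2.**

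| Row | Study A | M1 | M2 | M3 | M4 |
|---|---|---|---|---|---|
| Baseline own shoes | yes | yes | yes | yes | yes |
| Training | – | yes | yes | – | – |
| Retention | yes | yes | yes | – | – |
| Dual tasking, cognitive | – | yes | yes | yes | yes |
| Dual tasking, physical | – | yes | yes | yes | yes |

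**Required against scheduled at the two follow-up visits.**

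| Walk | Section 5.2 | Appendix A2 |
|---|---|---|
| Baseline | 2 of 2 | 2 of 2 |
| Learned pattern, single task, no feedback | 2 of 2 | 0 of 2 |
| Learned pattern, cognitive dual task | 2 of 2 | 2 of 2 |

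The with-and-without phrase in section 5.2 could apply to the replication alone or to the baseline walk as well. On either reading the learned pattern without the dual task is required.

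**Amount of data.** With 30 patients and 2 visits, up to 30 × 2 = 60 recordings would not be made. With the 24 patients whom the sample size requires, it would be 24 × 2 = 48.

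**What survives if A2 is followed.**
- Own-shoes baseline KAM is scheduled at every visit, so that half of the section 7.1 analysis is intact.
- Dual-task walks are scheduled at M2, M3 and M4, so the end of training can be compared with follow-up under one condition. The M1 dual-task value is less certain, because section 5.2 confines the dual-task steps to weeks 4 to 6 while A2 ticks them at M1, which is week 1.
- The powered comparison is pre versus post training. An exact noncentral-t calculation for a two-sided paired t-test at alpha 0.05 and effect size 0.6 gives N = 24 with power 0.804, matching section 4.4. It uses no follow-up value.
- The secondary objective on cognitive demand covers only the six-week training period, so it does not depend on M3 or M4.

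**Other A2 rows.**
- Section 5.2 says "Muscle strength will be assessed in study A and at the beginning and end of the training period" and at both follow-ups; A2 leaves that row empty at M2.
- Knee confidence is placed three ways: at every full assessment in section 3, in Study A in section 5.2, and at Study A, M3 and M4 in A2.

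**The case against.** The best defence is that the text is explicit and A2 is only an overview. Section 5.2 states the content of the follow-up visits plainly, section 3 calls M3 and M4 full assessments including KAM, and all gait measurement takes place in one laboratory. A2 is also visibly incomplete: EMG is required at several visits in section 5.2 but has no row. Absence from A2 is therefore weak evidence that a measurement is not intended. That stands as to intention. It does not remove the risk, because the protocol itself directs the reader to A2 for what is done at each visit, and 'Retention' is a row that is present and left empty at M3 and M4.

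A second defence is that 'Retention' is never defined. It is ticked only at visits that also have a learning or training row, so it may mean a trial at the end of a training session. Equating it with step 3 is an inference. If it means something else, however, no legible row schedules the required walk at M3 and M4. The table was also read from a damaged PDF, so a lost row cannot be fully excluded.

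Two stronger conclusions are tempting and are not supported. A reader might infer that no learned-pattern KAM at all would be collected after training, or that long-term retention could not be estimated. Neither follows: section 5.2 ties the cognitive dual task at follow-up to the learned pattern, A2 keeps that walk at M2 to M4, and retention under dual task can still be estimated. A reader might also infer that the sample size is compromised; it is not.

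**Conclusion.** The contradiction is real and touches the Study B primary analysis. The single-task learned-pattern KAM is required at both follow-up visits by section 5.2 and scheduled at neither by A2. If A2 is followed, that series stops at week 6 for every patient, and the dual-task values at M3 and M4 cannot replace it. The loss is confined to this one condition at these two visits; if section 5.2 is followed, nothing is lost.

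The conclusion assumes that the legible A2 rows are complete for the gait block and that no other row stands for this walk. Given the state of the table and the undefined row name, that is likely but not certain. Because the missing data would belong to the primary analysis and the correction is small, the passages should be reconciled before any follow-up visit is run from A2.

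The muscle-strength and knee-confidence discrepancies are minor. Section 5.1.3 lists muscle strength and self-reported stability among the other parameters, and section 7.3 treats strength and instability descriptively.

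**What to change.** Make A2 agree with section 5.2: tick the single-task, no-feedback walk with the learned pattern (step 3 of the Study B protocol) at M3 and M4. State in A2 what 'Retention' means, or rename the row to match step 3. Step 3 takes 15 + 45 = 60 seconds, so the cost is about 2 minutes per patient over two visits that already take place on the GRAIL, or 30 × 2 = 60 minutes of treadmill time over the whole study. The sample size does not change.

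In the same edit, reconcile the muscle-strength row with section 5.2 at M2, either by adding the tick or by dropping that time point from the text. For knee confidence, choose one schedule and put it in sections 3 and 5.2 and in A2; ticking M1 and M2 alone would still leave section 5.2 in conflict. If the text is changed rather than the schedule, these two corrections add no measurement time.
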